4.2. Inclusion Criteria

A subject must meet the following criteria to be eligible for inclusion in the study:

- Age 4 to 50 years (inclusive)
- Subject has a clinical history of allergy to cow's milk or milk-containing food
- Serum IgE to milk of $>4\text{ kUA/L}$ within the last 12 months and/or a SPT to milk $\geq 6\text{ mm}$ compared to a negative control
- Experience clinical reaction at or before 444 mg cumulative protein dose of cow's milk protein on Screening DBPCFC
- No clinical reaction observed during the placebo (oat) Screening DBPCFC
- Subjects/Caregivers must be trained on the proper use of the epinephrine auto-injector device to be allowed to enroll in the study.
- Subjects with other known food allergies must agree to eliminate these other food items from their diet so as not to confound the safety and efficacy data from the study
- Written informed consent from parent/guardian for minor subjects.
- Written assent from minor subjects as appropriate (eg, at and above the age of 7 years or the applicable age per local regulatory requirements)
- For women of childbearing potential (WOCBP), must agree to remain abstinent (refrain from heterosexual intercourse) or use acceptable contraceptive methods (barrier methods or oral, injected, or implanted hormonal methods of contraception or other forms of hormonal contraception that have comparable efficacy) during the treatment period and for 60 days after the last dose of study drug.

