8.2. Screening/Baseline Visits (V1)

The purpose of the screening period is to confirm eligibility to continue in the study. After obtaining informed consent/assent, subjects will be assessed for eligibility at a screening visit. Procedures for the screening visit may be spread over one to three separate days; these days do not need to be consecutive and can be spread out over the course of the entire screening window. All assessments must be completed no more than 6 months preceding initiation dupilumab/placebo (Visit 2, week 0), excluding the milk-specific IgE value which may be taken from the previous 12 months if needed to establish eligibility. Baseline/screening visit procedures following requirements below but conducted under a different protocol within the past 6 months (or 12 months for milk-specific IgE) prior to Visit 2 can be used towards this study. Visit 1 may occur on the same day as Visit 2, but must be completed prior to any Visit 2 procedure taking place.

The following procedures, assessments, and laboratory measures will be conducted to determine participant eligibility and collect baseline data:

- Consent and assent (conducted prior to any screening or study procedure)
- Medical history, including review of all food allergies
- Physical assessment
- Documentation of con meds and AEs
- Epinephrine auto-injector training with Food Allergy & Anaphylaxis Emergency Care Plan
- SPT to cow's milk (only if needed to determine eligibility)
- Lung function (spirometry, or peak flow if spirometry not available, applicable, or able to be performed reliably by the participant). If spirometry and peak flow are both unable to be completed, defer to clinician judgment
- Urine pregnancy test in women of childbearing potential (WOCBP)

Any of the above items may be repeated within the 6 months preceding initiation of study treatment if warranted, in the opinion of the investigator, by changes in the subject's clinical status. After all other eligibility criteria have been met, DBPCFCs to a cumulative 444 mg of milk and placebo (oat)

Double-Blind Placebo-Controlled Food Challenge (DBPCFC) at Screening

Participants meeting all other eligibility criteria will undergo DBPCFC to cow's milk protein and oat (placebo) during screening to confirm an allergy to milk. Randomization of the placebo and

milk challenge order and preparation of the challenge materials will be performed by trained unblinded study personnel.

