All food challenges will be performed under clinician supervision. Before each challenge, the subject will have a physical examination and lung function assessment conducted to ensure it is safe and appropriate to conduct the challenge. Each challenge will be supervised by a trained clinician who is blinded to the testing material. The screening DBPCFC will consist of 6 doses of milk protein given every 15-30 minutes in increasing amounts up to a cumulative total of 444 mg protein. The doses will be 1 mg, 3 mg, 10 mg, 30 mg, 100 mg, and 300 mg (see **Table 2**). The other challenge will consist of placebo material given also in 6 matching doses. Vital signs will be assessed every 15 minutes. If the study team suspects a reaction may be developing, they may exercise their clinical judgment to separate doses by up to an additional 30 minutes (one hour maximum between doses). The food challenge will be stopped and appropriately treated in the occurrence of two or more objective Grade 1 (Mild) reactions involving two or more organ systems; OR a persistent Grade 1 (Mild) reaction; OR any reaction of Grade 2 (Moderate) or higher severity. After the last dose of each DBPCFC, the subject will be monitored for 2 hours and then discharged from the clinic. Subjects will be considered to have tolerated the DBPCFC and excluded from the study if they do not experience any of the dose-limiting symptom criteria detailed above and tolerate all doses of the challenge.

Table 2. Dosing Regimen for DBPCFCs at Screening and Weeks 18/24

Dose #	Screening Milk OIT/Placebo Dose (mg protein)	Weeks 18/24 Milk OIT/Placebo Dose (mg protein)
1	1	10
2	3	30
3	10	100
4	30	300
5	100	600
6	300	1000
7	NA	2000

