Participants will receive their first dose of dupilumab/placebo in clinic at Visit 2. Participants will receive a second dose of dupilumab/placebo monotherapy at Visit 3 or 4, depending on dosing frequency determined by weight and age. Participants receiving dupilumab or placebo for dupilumab every 4 weeks will not return to clinic for Visit 3 as no dosing is scheduled at this time and associated procedures are not applicable.

Dupilumab and its matching placebo will be dosed according to the following algorithm:

- Participants aged 4-5 years old:
 - ≥ 5 to <15 kg will receive dupilumab 200 mg or placebo SC every 4 weeks following a loading dose of 400 mg on day 1 (Visit 2)
 - ≥ 15 to <30 kg will receive dupilumab 300 mg or placebo SC every 4 weeks following a loading dose of 600 mg on day 1 (Visit 2)
 - ≥ 30 kg will receive dupilumab 300 mg or placebo SC every 2 weeks following a loading dose of 600 mg on day 1 (Visit 2)
- Participants aged 6-17 years old:
 - ≥ 15 to <30 kg will receive dupilumab 300 mg or placebo SC every 4 weeks following a loading dose of 600 mg on day 1 (Visit 2)
 - ≥ 30 to <60 kg will receive dupilumab 200 mg or placebo SC every 2 weeks following a loading dose of 400 mg on day 1 (Visit 2)
 - ≥ 60 kg will receive dupilumab 300 mg or placebo SC every 2 weeks following a loading dose of 600 mg on day 1 (Visit 2)

- Participants aged 18 years or older will receive dupilumab 300 mg of placebo SC every 2 weeks following a loading dose of 600 mg on day 1 (Visit 2)

Prior to the first dose of study drug at Visit 2, participants will undergo blood draw and provide a stool/saliva sample (optional). Participants will be monitored for at least 30 minutes following each dose of dupilumab/placebo. Vital signs will be taken prior to dosing and again prior to discharge. Prior to the completion of Visit 2, participants will be trained on a Daily Dosing & Symptom Diary. Participants will be asked to bring their epinephrine auto-injector to each visit throughout the study in order to confirm they are equipped with an injector and that it is not expired. Participants with no injector or an injector that is expired or expiring prior to the next clinic visit will be provided with a prescription for a new epinephrine auto-injector.

Combination Therapy Phase (Visit 4 to Visit 10, Weeks 4 to 16)

Initial Dose Escalation Day (Visit 4, Week 4)

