Participants will return to clinic 2 weeks (± 5 days) from Visit 11a for Visit 12, and again in two weeks (± 5 days) for Visit 13. Visits 12 and 13 will be conducted in the same fashion and include all procedures as Visits 4 to 10 listed above, excluding administration of dupilumab/placebo. All participants not yet tolerating 1000 mg daily milk protein will continue to attempt dose escalations in clinic at each visit until a maximum daily dose of 1000 mg protein, as tolerated. Those escalating to and tolerating a daily dose of 1000 mg protein daily will remain at that dose for the remaining visits. The final possible up-dosing will occur at Visit 13.

Week 24 Double-Blind, Placebo-Controlled Food Challenge (Visits 14a and 14b)

At week 24, all subjects will undergo DBPCFCs up to 4040 mg milk protein (cumulative) and placebo to assess desensitization. The DBPCFCs will occur at two separate visits within the span of 10 days. Randomization of the placebo and milk challenge order and preparation of the challenge materials will be performed by trained unblinded study personnel. Both milk protein and oat will be concealed in an age-appropriate, non-offensive food vehicle that aids in masking the taste and appearance.

At Visit 14a, participants will return unused OIT doses remaining from the previously dispensed home dosing kit. Prior to the DBPCFC, accountability will be performed on the returned doses, when able, and the Daily Dosing & Symptom Diary will be reviewed to assess for AEs and home dosing compliance. Additionally, prior to the first dose of the Visit 14a DBPCFC, a blood draw will be performed and a stool/saliva sample will be collected (optional).

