13.6. Safety Analysis

13.6.1. Adverse Events

Definitions

For safety variables, 2 observation periods are defined:

- The pretreatment period is defined as the time from signing the ICF to before the first dose of study drug.
- The treatment period is defined as the day from first dose of study drug to the end of the study.

Treatment-emergent adverse events are defined as those that are not present at baseline or represent the exacerbation of a pre-existing condition during the on-treatment period.

Analysis

All AEs reported in this study will be coded using the currently available version of the CTCAE. Coding will be to lowest level terms. The verbatim text, the preferred term (PT), and the primary system organ class (SOC) will be listed.

Summaries of all AEs by treatment group will include:

- The number and percentage of subjects with at least 1 AE by SOC and PT
- AEs by severity, presented by SOC and PT
- AEs by relationship to treatment (related, not related), presented by SOC and PT
- Treatment-emergent AESIs (defined with a PT or a prespecified grouping)

Deaths and other SAEs, as well as AEs leading to permanent treatment discontinuation, will be listed and summarized by treatment group.

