13.7. Additional Statistical Data Handling Conventions

The following analysis and data conventions will be followed:

Definition of baseline:

- The baseline assessment will be the latest, valid pre-first-dose assessment available

General rules for handling missing data (for assessments other than efficacy):

- If the start date of an AE or concomitant medication is incomplete or missing, it will be assumed to have occurred on or after the intake of study medication, except if an incomplete date (e.g. month and year) clearly indicates that the event started prior to treatment. If the partial date indicates the same month or year of the intake of study medication date, then the start date by the study medication intake date will be imputed; otherwise, the missing day or month by the first day or the first month will be imputed.
- No imputations for missing laboratory data, vital sign data, or physical examination data will be made.

Unscheduled assessments:

- Extra assessments (laboratory data or vital signs associated with nonprotocol clinical visits or obtained in the course of investigating or managing AEs) will be included in listings, but not summaries. If more than 1 laboratory value is available for a given visit, the first observation will be used in summaries and all observations will be presented in listings.

Statistical considerations surrounding the premature termination of a study:

- If the study is terminated prematurely, only those parameters required for reporting to regulatory authorities will be summarized.

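### The same-day option for Visits 1 and 2 lets the only pre-dose mechanistic blood be drawn about 2 hours after the milk reaction that eligibility requires

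*Combined protocol and SAP*

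**What the plan says.** Section 8.2 on the two visits: "Visit 1 may occur on the same day as Visit 2, but must be completed prior to any Visit 2 procedure taking place". The same section places the screening challenges after all other eligibility criteria have been met, so a challenge is normally the last Visit 1 procedure.

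Section 4.2 makes a milk reaction a condition of entry: "Experience clinical reaction at or before 444 mg cumulative protein dose of cow's milk protein on Screening DBPCFC". Section 8.2 says a challenge that meets the stopping criteria is stopped and treated. Observation is 2 hours after the last dose, and Section 3.1 adds that the participant must be clinically stable at discharge.

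At Visit 2, Section 8.3 says: "Prior to the first dose of study drug at Visit 2, participants will undergo blood draw". Table 4 (Section 8.6) puts mechanistic blood at Visits 2, 4, 11a and 14a and not at Visit 1. It puts the milk skin prick test at Visit 1 (only if needed for eligibility), 2, 11a and 14a, and randomisation and the first study drug dose at Visit 2.

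At week 24, Section 8.3 says: "prior to the first dose of the Visit 14a DBPCFC, a blood draw will be performed". The week 18 text has the same order.

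Section 13.7 defines baseline: "The baseline assessment will be the latest, valid pre-first-dose assessment available". Section 13.6.1 defines the safety window: "The treatment period is defined as the day from first dose of study drug to the end of the study".

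**The concern.** The exploratory endpoints in Section 3.5.2 include change from baseline to week 24 in the basophil activation threshold, in milk-specific and total IgE and IgG4, and in skin test response. For the blood endpoints, the Visit 2 draw is the only sample before study drug, so there is no fallback if it is taken under unusual conditions. Sections 1.1 and 9.2 themselves describe basophils as taking part in the acute reaction that the challenge provokes.

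Under the same-day option some participants would have their baseline taken shortly after a provoked and treated reaction. Others would have it taken at rest, up to 6 months after the challenge. All would have their week 18 and week 24 blood taken before a challenge.

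There is also a safety-data consequence. Section 1.2.3.1 separates injection from milk dosing by at least 30 minutes so that adverse events can be attributed to one or the other. A first injection a few hours after a milk reaction works against that aim.

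**Working it through.** **1. The plan's own figure.** Section 8.2: "The doses will be 1 mg, 3 mg, 10 mg, 30 mg, 100 mg, and 300 mg". The sum is 1 + 3 + 10 + 30 + 100 + 300 = 444 mg, as stated.

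**2. Does a same-day Visit 2 fit into a day?** Six doses have five intervals. Time for one full challenge plus observation = 5 × g + 120 minutes, where g is the dose interval (15 to 30 minutes, at most 60).

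| g (min) | One challenge + 2 h | Oat then milk, each + 2 h |
|---|---|---|
| 15 | 75 + 120 = 195 min = 3.25 h | 6.5 h |
| 30 | 150 + 120 = 270 min = 4.5 h | 9.0 h |
| 60 | 300 + 120 = 420 min = 7.0 h | 14.0 h |

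These are upper limits for milk, because a challenge that stops at an earlier dose is shorter. If oat was done on an earlier day, milk and Visit 2 fit on one day. With both challenges on one day, Visit 2 still fits at the shorter intervals.

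**3. Which challenge order is exposed?** Section 3.6.1 says the order is chosen at random.
- *Milk first.* The participant reacts. Table 4 footnote 11 then bars the oat challenge from the same visit, and Section 3.1 spaces the two by at least 48 hours if the reaction was treated. Visit 2 must wait for oat, so it is separated from the milk reaction.
- *Milk last.* No later challenge remains, so the 48-hour rule has nothing to act on. The only general waits before Visit 2 are the 2 hours of observation and clinical stability at discharge.

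**4. Blood: baseline against follow-up.** In a milk-last, same-day participant the baseline draw can come 2 hours after the last milk dose. At weeks 18 and 24 it comes before the first challenge dose. Section 8.3 and Table 4 footnote 8 order the Visit 2 draw before study drug, but nothing orders it relative to the milk challenge.

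**5. Skin test: sections side by side.** Section 7.2 lists antihistamines and short-acting beta-agonists among the rescue medications. Sections 4.3 and 7.1.3 list use of oral antihistamines within five half-lives, or of beta-agonists within 12 hours, before skin testing as grounds for exclusion or removal. Section 7.1.2 repeats the antihistamine washout. So after oral antihistamine rescue, a same-day Visit 2 skin test conflicts with all three sections. After beta-agonist rescue it conflicts with 4.3 and 7.1.3. Section 8.2 also has the participant discharged after the challenge, and Section 8.3 has them coming back for Visit 2. Neither fits well with one combined day, though neither forbids it.

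**6. Adverse events.** Section 11.2.1 records expected challenge symptoms within two hours as dosing reactions and later symptoms as adverse events. The treatment period starts at the first dose. A challenge symptom that first appears after the injection is absent at baseline and so meets the treatment-emergent definition in Section 13.6.1.

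**7. How many?** Number exposed = 116 × u × s, where u is the share having Visit 2 on the day of their last screening challenge and s is the share with milk last. Neither is stated. If s = 0.5 (1:1 order, an assumption), the ceiling at u = 1 is 116 × 0.5 = 58. Purely as illustration, u = 0.10 gives 5.8 and u = 0.30 gives 17.4. These values of u have no source in the documents.

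**The case against.** The strongest reply is that the path is narrow and partly guarded. It mainly needs milk last, on the final screening day, with Visit 2 that same day. Section 8.2 allows screening over one to three days and reuse of procedures from another protocol within 6 months, so many same-day visits may involve no milk challenge at all. This stands and limits the point.

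Several stronger readings are tempting, and the documents do not support them.
- *Every participant's baseline is affected, because every participant reacts.* Only those who use the option with milk last are exposed.
- *Section 13.7 forces a medicated Visit 2 skin test to replace an earlier clean one.* The rule requires the assessment to be valid. The term is not defined, but it leaves room to reject such a test.
- *Anyone given rescue medication must be removed from the trial.* Section 7.1 counts as concomitant only treatment given from the first study drug dose, or started earlier and ongoing. One rescue dose at Visit 1 may fall outside that. The sections conflict, but the consequence is not settled.
- *Follow-up skin tests are also done before the challenge.* The order is explicit for blood only.
- *The assays are known to shift.* The documents give no size for any change in basophil threshold, IgE, IgG4 or skin response within hours of a challenge.
- *Challenge symptoms in general will be counted against study drug.* Expected symptoms within two hours are dosing reactions, symptoms already present at baseline are not treatment-emergent unless they worsen, and Section 11.3.2 allows attribution to a procedure. Only new late symptoms remain.

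It can also be said that this is merely missing detail in exploratory work. That does not fully answer the point: the same-day permission is explicit, and following it as written gives a poorer baseline that cannot be recovered later.

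**Conclusion.** The point holds in limited form. The protocol expressly permits a sequence in which the sole pre-dose mechanistic sample follows a required milk reaction by about 2 hours, the reverse of the order it specifies at weeks 18 and 24. The same permission sits badly with the skin test washouts and with the text that has participants discharged and returning for Visit 2.

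Exposure arises before treatment is assigned, so it should be balanced between arms in expectation. The result is added noise and a shifted baseline in the basophil, antibody and skin test endpoints, which are exploratory and analysed descriptively (Section 13.5.3). A smaller effect is ambiguity over late adverse events just after the first injection. A reader might infer bias in the treatment comparison or in the main result, but the documents do not support this. The week 18 responder endpoint uses none of these baselines, and the cumulative tolerated dose takes its baseline from the screening challenge itself.

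The size cannot be fixed. The number exposed depends on uptake and challenge order, and the assay effect is not documented. The recommendation rests on the low cost of the remedy, not on a demonstrated large effect.

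**What to change.** Amend Section 8.2 and add a Table 4 footnote stating that baseline mechanistic blood and the baseline skin test are taken either before the first milk challenge dose or on a day without a milk challenge, with the existing medication washouts still applying. The first choice needs an exception to the rule that Visit 1 is completed before any Visit 2 procedure.

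Reconcile the same-day sentence in Section 8.2 with the discharge wording there, the return for Visit 2 in Section 8.3, and the skin test medication limits in Section 7.1.3 (also in 4.3 and 7.1.2). Any interval between the milk reaction and the first study drug dose is for the sponsor to set, and none is proposed here. The 48 hours in Section 3.1 concerns spacing between challenges and should not be read as such an interval.

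The cost is one sentence and one footnote. In practice it means at most one extra clinic day for participants who would have combined the visits or, if sampling moves ahead of the challenge, some samples drawn from people who then prove ineligible.

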8.3. Active Study Phase Visits

Visits throughout the study will occur every two weeks plus or minus 5 days (i.e. 9 to 19 days apart), excluding the second food challenges at Weeks 18 and 24. The following procedures, assessments, and laboratory measures will be conducted in clinic at each study visit prior to any study product dosing:

- Physical assessment
- Food Allergy Quality of Life Questionnaires (FAQLQ) (only at Visits 2, 11a, and 14a)
 - The applicable versions of the questionnaire will be administered to the participant and guardian for completion as per investigator discretion; these may include:
 - FAQLQ - Child Form (participants aged 8-12 years; [Flokstra-de Blok, DunnGalvin 2009](#))
 - FAQLQ - Teenager Form (participants aged 13-17 years; [Flokstra-de Blok 2008](#))
 - FAQLQ - Adult Form (participants aged 18 years or older; [Flokstra-de Blok, van der Meulen 2009](#))
 - FAQLQ - Parent Form (guardians of participants aged 4-12 years; [DunnGalvin 2009](#))

- FAQLQ - Parental Burden (guardians of participants aged 4-17 years; [Cohen 2004](#))
- Eosinophilic Esophagitis Questionnaires (only at Visits 2, 4, 10, and 14a)
 - The applicable versions of the questionnaire will be administered to the participant and/or guardian for completion as per investigator discretion; these may include:
 - Pediatric Eosinophilic Esophagitis Symptom Severity Module v2.0 - Parent Report for Children and Teens (Ages 2-17) ([Franciosi 2011](#))
 - Pediatric Eosinophilic Esophagitis Symptom Severity Module v2.0 - Children and Teens Report (Ages 8-17) ([Franciosi 2011](#))
 - Eosinophilic Esophagitis Activity Index (Participants aged 18 years or older) ([Schoepfer 2014](#))
- Lung function (spirometry or peak flow if spirometry not available, applicable, or able to be performed reliably by the participant). If spirometry and peak flow are both unable to be completed, defer to clinician judgment.
- Documentation (and review, when appropriate) of con meds and AEs
- Urine pregnancy test in WOCBP

Active Run-In Phase (Visits 2 & 3, Weeks 0 to 4)

Participants who meet all eligibility criteria at screening will return to clinic at Visit 2. Those continuing to meet eligibility criteria at Visit 2 will be randomized by the site unblinded pharmacist(s) in a 1:1 ratio to begin receiving dupilumab or placebo every two to four weeks in blinded fashion.

Participants will receive their first dose of dupilumab/placebo in clinic at Visit 2. Participants will receive a second dose of dupilumab/placebo monotherapy at Visit 3 or 4, depending on dosing frequency determined by weight and age. Participants receiving dupilumab or placebo for dupilumab every 4 weeks will not return to clinic for Visit 3 as no dosing is scheduled at this time and associated procedures are not applicable.

Dupilumab and its matching placebo will be dosed according to the following algorithm:

- Participants aged 4-5 years old:
 - ≥ 5 to <15 kg will receive dupilumab 200 mg or placebo SC every 4 weeks following a loading dose of 400 mg on day 1 (Visit 2)
 - ≥ 15 to <30 kg will receive dupilumab 300 mg or placebo SC every 4 weeks following a loading dose of 600 mg on day 1 (Visit 2)
 - ≥ 30 kg will receive dupilumab 300 mg or placebo SC every 2 weeks following a loading dose of 600 mg on day 1 (Visit 2)
- Participants aged 6-17 years old:
 - ≥ 15 to <30 kg will receive dupilumab 300 mg or placebo SC every 4 weeks following a loading dose of 600 mg on day 1 (Visit 2)
 - ≥ 30 to <60 kg will receive dupilumab 200 mg or placebo SC every 2 weeks following a loading dose of 400 mg on day 1 (Visit 2)
 - ≥ 60 kg will receive dupilumab 300 mg or placebo SC every 2 weeks following a loading dose of 600 mg on day 1 (Visit 2)

- Participants aged 18 years or older will receive dupilumab 300 mg of placebo SC every 2 weeks following a loading dose of 600 mg on day 1 (Visit 2)

Prior to the first dose of study drug at Visit 2, participants will undergo blood draw and provide a stool/saliva sample (optional). Participants will be monitored for at least 30 minutes following each dose of dupilumab/placebo. Vital signs will be taken prior to dosing and again prior to discharge. Prior to the completion of Visit 2, participants will be trained on a Daily Dosing & Symptom Diary. Participants will be asked to bring their epinephrine auto-injector to each visit throughout the study in order to confirm they are equipped with an injector and that it is not expired. Participants with no injector or an injector that is expired or expiring prior to the next clinic visit will be provided with a prescription for a new epinephrine auto-injector.

Combination Therapy Phase (Visit 4 to Visit 10, Weeks 4 to 16)

Initial Dose Escalation Day (Visit 4, Week 4)

At week 4 (Visit 4), participants will return to clinic undergo an initial dose escalation to determine the dose in which they will begin daily milk protein OIT. As detailed above, the subject will have a physical examination and lung function assessment conducted to ensure it is safe and appropriate to proceed with the escalation. Prior to the first dose of study drug at Visit 4, participants will undergo blood draw. Dupilumab/placebo will be administered in clinic at least 30 minutes prior to the first dose of milk OIT. Vital signs will be taken prior to dupilumab/placebo dosing, and again prior to the start of the initial dose escalation.

The initial dose escalation will consist of three doses of milk protein given every 15 to 30 minutes in increasing amounts up to a cumulative total of 35 mg milk protein. The doses will be 5, 10, and 20 mg protein mixed in an age-appropriate, non-offensive food vehicle (**Table 3**). The escalation may be stopped at the occurrence of any AE per clinician discretion. Participants unable to tolerate 5 mg milk protein during the initial dose escalation will be considered treatment failures.

Table 3. Initial Dose Escalation Regiment

Dose #	Milk OIT Dose (mg protein)
1	5
2	10
3	20

Each participant will be monitored for a minimum of 2 hours following the last dose administered and discharged from the clinic only when deemed clinically stable by a study clinician. Participants will be discharged with a two-week supply of milk OIT doses for daily home-dosing at the highest non-cumulative dose tolerated (i.e. 5, 10, or 20 mg protein) during escalation. The first dose will be taken at home the day after Visit 4, and the participant will return to clinic in two weeks, plus or minus 5 days, to attempt to escalate their daily dose according to **Table 1**. Daily Dosing & Symptom Diary and epinephrine auto-injector training will be repeated prior to discharge.

For all milk OIT doses, the daily home dose should be taken as part of a meal at a consistent time (within 24±2 hours of the previous day's dose), and it is critical to take the dose every day unless otherwise directed. Doses should be separated by at least 12 hours. Vigorous exercise is not permitted for at least 2 hours after the dose of OIT, and there must be at least 1 hour between vigorous exercise and taking the dose. Allergic reactions are still possible when exercise takes place more than 2 hours after the dose. Prior to the completion of Visit 4, participants will be trained on proper epinephrine use (**Appendix 2**).

Combination Therapy (Visit 4 to Visit 10, Weeks 4 to 16)

Following the initial dose escalation (Visit 4), participants will return to clinic every two weeks (±5 days) to gradually increase their daily milk OIT dose to a maximum of 1000 mg protein daily, as tolerated, following a standardized up-dosing regimen (**Table 1**). As detailed above, the subject will have a physical examination and lung function assessment conducted to ensure it is safe and appropriate to proceed with the escalation.

At each visit, participants should return unused OIT doses remaining from the previously dispensed home dosing kit. Prior to the in-clinic dose, accountability should be performed on the returned doses, when possible, and the Daily Dosing & Symptom Diary will be reviewed to assess for AEs and home dosing compliance to ensure the participant meets the criteria for up-dosing. If the participant does not return the unused doses from the previous kit (e.g. they forget the doses at home or the doses are inadvertently lost), review of the Daily Dosing & Symptom Diary is sufficient to evaluate participant compliance. Effort should be made to have the participant return the unused doses at their earliest ability.

Subjects must withhold their daily home dose and any prophylactic antihistamines on the day of the in-clinic dosing but should take all other prescribed medications, except where prohibited in this protocol. Dosing and AEs will be monitored and documented during each in-clinic OIT dosing. The participant will be observed following the in-clinic dose and dispensed a new kit of OIT for home dosing prior to discharge.

During combination therapy, participants in **Cohort A** will continue to receive dupilumab, while those in **Cohort B** continue to receive placebo for dupilumab. Dupilumab/placebo doses will be administered at least 30 minutes prior to the in-clinic milk OIT dosing every two to four weeks. The last dose of dupilumab/placebo given in the study will be administered at week 16 (Visit 10).

Washout Phase (Visit 10 to Visit 14b, Weeks 16 to 24)

The final administration of dupilumab at week 16 will mark the beginning of the washout phase. Daily Milk OIT will be continued alone for 8 weeks, with DBPCFCs conducted at weeks 18 and 24.

Week 18 Double-Blind, Placebo-Controlled Food Challenge (Visits 11a and 11b)

At week 18, under clinician supervision, all subjects will return to clinic to undergo DBPCFCs up to 4040 mg milk protein (cumulative) and placebo to assess desensitization. The DBPCFCs will occur at two separate visits within the span of 7 days. Randomization of the placebo and milk challenge order and preparation of the challenge materials will be performed by trained unblinded study personnel. Both milk protein and oat will be concealed in an age-appropriate, non-offensive food vehicle to aid in masking the taste and appearance.

At Visit 11a, participants will return unused OIT doses remaining from the previously dispensed home dosing kit. Prior to the DBPCFC, accountability will be performed on the returned doses, when able, and the Daily Dosing & Symptom Diary will be reviewed to assess for AEs and home dosing compliance. Additionally, prior to the first dose of the Visit 11a DBPCFC, a blood draw will be performed.

As detailed above, the subject will have a physical examination and lung function assessment conducted to ensure it is safe and appropriate to proceed with the escalation. Vital signs will be assessed every 15 minutes. Each DBPCFC will consist of 7 doses (milk protein or placebo), given every 15 to 30 minutes: 10 mg, 30 mg, 100 mg, 300 mg, 600 mg, 1000 mg, and 2000 mg protein, resulting in a total challenge of up to 4040 mg milk protein (cumulative). If the study team suspects a reaction may be developing, they may exercise their clinical judgment to separate doses by up to an additional 30 minutes (1 hour maximum between doses). The food challenge will be stopped and appropriately treated in the occurrence of two or more objective Grade 1 (Mild) reactions involving two or more organ systems; OR a persistent Grade 1 (Mild) reaction; OR any reaction of Grade 2 (Moderate) or higher severity. The subject's tolerance to milk allergen, or cumulative tolerated dose (CTD), is defined as the highest cumulative protein dose in which the subject does not experience any of the dose-limiting symptom criteria listed above. After the last dose of each DBPCFC, the subject will be monitored for a minimum of 2 hours and then discharged from the clinic only when deemed clinically stable by a study clinician. The food challenges can be performed on consecutive days if no reactions have occurred. If a reaction occurs and is treated, then the challenges should be at least 48 hours apart.

Participants will be discharged with a new kit of home OIT doses at Visit 11a at the same dose as that previously dispensed and tolerated at Visit 10. Participants will skip their daily home dose of milk OIT on DBPCFC days (Visit 11a and b), but will take their home dose on days between the DBPCFCs if the DBPCFCs are not on consecutive days.

Washout Phase (Non-DBPCFC Visits: Visits 12 and 13)

Participants will return to clinic 2 weeks (± 5 days) from Visit 11a for Visit 12, and again in two weeks (± 5 days) for Visit 13. Visits 12 and 13 will be conducted in the same fashion and include all procedures as Visits 4 to 10 listed above, excluding administration of dupilumab/placebo. All participants not yet tolerating 1000 mg daily milk protein will continue to attempt dose escalations in clinic at each visit until a maximum daily dose of 1000 mg protein, as tolerated. Those escalating to and tolerating a daily dose of 1000 mg protein daily will remain at that dose for the remaining visits. The final possible up-dosing will occur at Visit 13.

Week 24 Double-Blind, Placebo-Controlled Food Challenge (Visits 14a and 14b)

At week 24, all subjects will undergo DBPCFCs up to 4040 mg milk protein (cumulative) and placebo to assess desensitization. The DBPCFCs will occur at two separate visits within the span of 10 days. Randomization of the placebo and milk challenge order and preparation of the challenge materials will be performed by trained unblinded study personnel. Both milk protein and oat will be concealed in an age-appropriate, non-offensive food vehicle that aids in masking the taste and appearance.

At Visit 14a, participants will return unused OIT doses remaining from the previously dispensed home dosing kit. Prior to the DBPCFC, accountability will be performed on the returned doses, when able, and the Daily Dosing & Symptom Diary will be reviewed to assess for AEs and home dosing compliance. Additionally, prior to the first dose of the Visit 14a DBPCFC, a blood draw will be performed and a stool/saliva sample will be collected (optional).

As detailed above, the subject will have a physical examination and lung function assessment conducted to ensure it is safe and appropriate to proceed with the escalation. All food challenges will be performed under clinician supervision. Vital signs will be assessed every 15 minutes. The DBPCFC will consist of 7 doses (milk protein or placebo), given every 15 to 30 minutes: 10 mg, 30 mg, 100 mg, 300 mg, 600 mg, 1000 mg, and 2000 mg protein, resulting in a total challenge of up to 4040 mg milk protein (cumulative). If the study team suspects a reaction may be developing, they may exercise their clinical judgment to separate doses by up to an additional 30 minutes (1 hour maximum between doses). The food challenge will be stopped and appropriately treated in the occurrence of two or more objective Grade 1 (Mild) reactions involving two or more organ systems; OR a persistent Grade 1 (Mild) reaction; OR any reaction of Grade 2 (Moderate) or higher severity. After the last dose of each DBPCFC, the subject will be monitored for a minimum of 2 hours and then discharged from the clinic only when deemed clinically stable by a study clinician. The food challenges can be performed on consecutive days if no reactions have occurred. If a reaction occurs and is treated, then the challenges should be at least 48 hours apart.

Participants will be discharged with a new kit of home OIT doses at Visit 14a at the same dose as that previously dispensed and tolerated at Visit 13. Participants will skip their daily home dose of milk OIT on DBPCFC days (Visit 14a and b), but will take their home dose on days between the DBPCFCs if the DBPCFCs are not on consecutive days. At Visit 14b, participants will return unused OIT doses remaining from the home dosing kit dispensed at Visit 14a. Accountability will be performed on the returned doses, when able, and the Daily Dosing & Symptom Diary will be reviewed to assess for AEs and home dosing compliance.

The conclusion of the second DBPCFC and Visit 14b will mark study completion for each participant. Participants can exit the trial at Visit 14b to meet the study completion criteria.

